3.3.2. Study Day and Time to Event

Use of "Day 29" or "Day 15" are references to actual study days and represent 28 and 14 days post-randomization, respectively. References to visits such as "Study Visit Day 29" and "Study Visit Day 15" pertain to protocol-defined visits which may occur on any day within the defined visit window and not necessarily on Day 29 and Day 15.

Time-to-event endpoints are based on actual study days, e.g., Day 29 or Day 15. Endpoints that are not specifically defined as a time-to-event are based on Study Visits, irrespective of the study day upon which the visit was conducted. As a result, time-to-event endpoints at Day 15 and Day 29 may not match corresponding Clinical Status Ordinal Scores at Study Visit Day 15 and Study Visit Day 29. For example, all subjects with Clinical Status in Category 7 or 8 recorded for Study Visit Day 29 performed on or after Day 31 may not count as events by Day 29 unless there is additional corroborating data (e.g., Death or Supplemental Oxygen Case Report Forms).

3.3.3. Mechanical Ventilation-Free Survival at Day 29

Subjects who do not report an ordinal score in Category 8 (Death) or Category 7 (hospitalized on invasive mechanical ventilation or ECMO) at any point following randomization up to and including Day 29 will be

considered to have survived free from mechanical ventilation. The proportion of subjects who survive through Day 29 free from mechanical ventilation will be estimated using a Kaplan-Meier method, allowing definition of time-to-event and time-to-censoring for all subjects.

The time-to mechanical ventilation or death is defined as the elapsed time in days from randomization to the earliest day at which the subject requires mechanical ventilation or dies. The day the subject requires mechanical ventilation is defined as the first day reporting an ordinal score in Category 7. Note (as in Section 3.3.4), this should be the date the subject is assessed, and not the date the score is reported. The time-to-event for subjects discharged to hospice or other end-of-life care prior to Day 29, but for whom a death date is unknown and with Day 60 data unavailable, will be the number of days from randomization to discharge.

Subjects with Day 29 ordinal score in Categories 6, 5, 4, 3, 2 or 1 will be considered censored on Day 29, if Category 7 was never experienced during the 28 days on study. Subjects completing the Day 29 Study Visit within window, but after Day 29, for which the Day 29 assessment can be completed or confirmed in Categories 6, 5, 4, 3, 2, or 1 will be considered censored on Day 29. Subjects who withdraw from the study or are lost-to-follow-up while hospitalized, prior to reporting a Clinical Status score in Category 7 or 8 will be censored at the date of their last Clinical Status assessment. Subjects who are discharged from hospital (but not to hospice or other end-of-life care) and are not hospitalized at the last contact, who do not have a Day 29 Ordinal Score will be considered censored at Day 29 (i.e., 28 days after randomization). If a subject has a gap in Ordinal Score data available while hospitalized (e.g., the subject is transferred to another hospital or hospice, re-admitted to another facility), the subject may be reviewed by the blinded Endpoint Review Committee to assess whether any data suggests the subject may have progressed to mechanical ventilation in the interim time period. Additionally, if a treated subject terminates early from the study while hospitalized (e.g., due to worsening condition) and without observed progression to mechanical ventilation, the subject's data will be reviewed by the blinded Endpoint Review Committee. Subjects not completing Day 29 or discharged to hospice or other end-of-life care prior to Day 29 with a death date unknown but completing Day 60 will be reviewed by the blinded Endpoint Review Committee to assess whether the Day 60 data impacts handling of the subject for the Day 29 timepoint. Other special cases may also be included for review by the blinded Endpoint Review Committee, as needed.

3.3.4. Clinical Status Ordinal Score at Specific Timepoints

The Primary Endpoint, Key Secondary Endpoint, and several other Secondary Endpoints rely on evaluation of the Clinical Status ordinal score at specific days. For these endpoints, the Study Visit Day is the timepoint of interest, not the actual study day (e.g., Study Visit Day 29 as opposed to study day 29). The Clinical Status Score collected at the Study Visit corresponding to the specific endpoint will be used for the outcome. Specifically, results from Study Visit Day 29 will be used for the Primary Endpoint and results from Study Visit Day 15 will be used for the Key Secondary Endpoint, with these and other Study Visit Days (3, 5, 8, 11, 22) used for other Secondary Endpoints. For analyses involving Clinical Status at specific timepoints, imputation of missing scores may be performed following the rules described in Section 6.5.

3.3.5. Progression to Clinical Status Category 6, 7, or 8 by Day 29

This Secondary Endpoint will be assessed similarly to Mechanical Ventilation-free survival (Section 3.3.2), but the event of interest is any report of a Clinical Status ordinal score in Category 8 (Death), Category 7 (invasive mechanical ventilation or ECMO), or Category 6 (non-invasive ventilation or high-flow oxygen device). This endpoint will only be assessed in those with actual baseline Clinical Status in Category 5 (hospitalized, requiring supplement oxygen).

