3.2. Endpoints

The 8-point ordinal scale is utilized as the principal clinical assessment tool during the study and is the basis for the primary and multiple secondary endpoints. The 8-point ordinal scale is defined as (worst to best):

Category 8: Death;

Category 7: Hospitalized, on invasive mechanical ventilation or ECMO;

Category 6: Hospitalized, on non-invasive ventilation or high flow oxygen devices;

Category 5: Hospitalized, requiring supplemental oxygen;

Category 4: Hospitalized, not requiring supplemental oxygen - requiring ongoing medical care (COVID-19 related or otherwise);

Category 3: Hospitalized, not requiring supplemental oxygen - no longer requiring ongoing medical care. This would include those kept in hospital for quarantine/infection control, awaiting bed in rehabilitation facility or homecare, etc.;

Category 2: Not hospitalized, but has new or increased limitation on activities and/or new or increased requirement for home oxygen over baseline, pre-COVID-19 status;

Category 1: Not hospitalized, patient is back to their baseline, pre-COVID-19 status, that is, no new or increased limitations on activities and no new or increased oxygen use compared with baseline.

Primary Endpoint

Mechanical ventilation free survival by Day 29 will be assessed as the proportion of subjects not meeting criteria for either of the following categories on the 8-point ordinal scale at any time before or at Day 29.:

Category 8: Death

Category 7: Hospitalized, on invasive mechanical ventilation or ECMO

Secondary Endpoints

The key secondary endpoint is the proportion of subjects meeting criteria for each of the 8-point ordinal scale categories on Day 15.

Other Secondary Endpoints are:

- Proportion of subjects not meeting criteria for one of the following ordinal scale categories at any time by Day 29

Category 8: Death

Category 7: Hospitalized, on invasive mechanical ventilation or ECMO

Category 6: Hospitalized, on non-invasive ventilation or high flow oxygen devices

- Days from randomization and cause of death (if applicable).

- The time to recovery defined as the days from randomization to the first day on which the subject satisfies the criteria for any of the following three categories on the 8-point ordinal scale at any time before or at Day 29:

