4.2.6. Blinding

As both arms are receiving remdesivir, the remdesivir product is not blinded and study infusions can be labeled accordingly. The baricitinib/placebo component is blinded. Baricitinib and placebo tablets are identical in appearance. The dexamethasone/placebo IV component is blinded. Dexamethasone and intravenous placebo are identical in appearance.

Unblinding of the study will occur after all subjects enrolled have reached the end of study, these visits are monitored, and data is cleaned or if the DSMB recommends unblinding. Data through Day 29 will be locked prior to the completion and lock of Day 60 data. DMID and the SDCC will be unblinded after the Day 29 database lock. Clinical sites will not be unblinded to subject-level treatment assignments until after the Day 60 database lock.

If a subject's clinical status worsens to require mechanical ventilation (ordinal 7), the treating clinician may request unblinding in order to use the prior treatment assignment to inform future treatment. See protocol Appendix D Section 6.3.2.2.

If a Serious Adverse Event occurs, that is thought to be related to the study drug, and the treating clinician believes that knowledge of the treatment arm may change the therapy provided to the patient, the individual subject can be unblinded. If unblinded for SAE, the investigator may decide to have the blinded study product and/or remdesivir infusions discontinued based on the adverse event that led to unblinding and the benefit-risk analysis. See protocol Appendix D Section 6.3.2.3.

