		# of Subj.	# of Dev.	# of Subj.	# of Dev.	# of Subj.	# of Dev.	# of Subj.	# of Dev.	# of Subj.	# of Dev.	# of Subj.	# of Dev.	# of Subj.	# of Dev.	# of Subj.	# of Dev.	# of Subj.	# of Dev.
Treatment administration	Any type	x	x	x	x	x	x	x	x	x	x	x	x	x	x	x	x	x	x
	Required procedure done incorrectly	x	x	x	x	x	x	x	x	x	x	x	x	x	x	x	x	x	x
	Study product temperature excursion	x	x	x	x	x	x	x	x	x	x	x	x	x	x	x	x	x	x
	Other	x	x	x	x	x	x	x	x	x	x	x	x	x	x	x	x	x	x
Blinding policy/procedure	Any type	x	x	x	x	x	x	x	x	x	x	x	x	x	x	x	x	x	x
	Treatment unblinded	x	x	x	x	x	x	x	x	x	x	x	x	x	x	x	x	x	x
	Other	x	x	x	x	x	x	x	x	x	x	x	x	x	x	x	x	x	x

^a[X] additional subjects are included in the 'All Subjects' column that were enrolled with a baseline ordinal score of 4. [Include as applicable]

Table with similar format:

Table 14: Distribution of Major Subject Specific Protocol Deviations by Category, Type, Treatment Group, and Actual Baseline Ordinal Score – mITT Population

Table 15: Mechanical Ventilation-free Survival by Day 29 by Treatment Group and Actual Baseline Ordinal Score

Analysis Population	Treatment Group	Actual Baseline Ordinal Score	Number Subjects requiring Mechanical Ventilation by Day 29	Number Subjects Dying by Day 29	Day 29 Mechanical Ventilation-Free Survival		HR		P-value
					Estimate	95% CI	Estimate	95% CI	
mITT Population	Baricitinib + PBO + RDV (N=X)	5	x	x	x.x	x.x, x.x	x.xx	x.xx, x.xx	--
	PBO + Dexamethasone + RDV (N=X)		x	x	x.x	x.x, x.x			
	Baricitinib + PBO + RDV (N=X)	6	x	x	x.x	x.x, x.x	x.xx	x.xx, x.xx	--
	PBO + Dexamethasone + RDV (N=X)		x	x	x.x	x.x, x.x			
	Baricitinib + PBO + RDV (N=X)	Baseline Clinical Status 5 or 6	x	x	x.x	x.x, x.x	x.xx	x.xx, x.xx	0.xxx
	PBO + Dexamethasone + RDV (N=X)		x	x	x.x	x.x, x.x			
	Baricitinib + PBO + RDV (N=X)	Any Baseline Ordinal Score	x	x	x.x	x.x, x.x	x.xx	x.xx, x.xx	--
	PBO + Dexamethasone + RDV (N=X)		x	x	x.x	x.x, x.x			

Repeat for the As Treated Population and ITT population.

N= Number of subjects in the specified treatment group, actual baseline ordinal score, and analysis population.

n = Number of subjects.

Mechanical Ventilation-Free Survival are Kaplan-Meier Estimates at Day 29 study visit

HR is the ratio of the hazard of mechanical ventilation or death in each treatment group estimated from the Cox model. The ratio is to PBO + Dexamethasone + RDV to Baricitinib + PBO + RDV.

HRs for the 'combined ordinal score groups' are the hazard ratio from the stratified Cox Model.

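### SAP Section 3.3.4 assigns the primary endpoint to the Study Visit Day 29 score, contradicting the any-time-by-actual-Day-29 definition in Sections 3.2, 3.3.2, 3.3.3 and 8.1.1

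*SAP*

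**What the plan says.** **Definition by actual day.** Section 3.2 counts a primary event if the subject meets Category 7 or 8 "at any time before or at Day 29". Section 3.3.2 explains that Day 29 means the actual study day, 28 days after randomization, and adds: "Time-to-event endpoints are based on actual study days, e.g., Day 29 or Day 15". Only endpoints not defined as time-to-event use Study Visits. Section 3.3.3 applies this to the primary endpoint: the subject must be free of Category 7 and 8 "at any point following randomization up to and including Day 29", and event time is the first day in Category 7 or the day of death. Section 8.1.1 tests the difference in Kaplan-Meier estimates at t = 28.

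**Definition by visit.** Section 3.3.4 lists the primary endpoint among those for which the Study Visit Day, and not the actual study day, is the timepoint, with the score collected at that visit as the outcome. It then repeats: "Specifically, results from Study Visit Day 29 will be used for the Primary Endpoint". The Table 15 footnote uses the same language: "Mechanical Ventilation-Free Survival are Kaplan-Meier Estimates at Day 29 study visit". Section 8.1.2.2 and the Table 23 footnote do so for the endpoint of not progressing to Category 6, 7 or 8.

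**Day 60 data and unblinding.** Section 3.3.3 sends certain subjects without complete Day 29 information to the blinded Endpoint Review Committee "to assess whether the Day 60 data impacts handling of the subject for the Day 29 timepoint". Section 4.2.6 locks the Day 29 data before the Day 60 data are complete and states: "DMID and the SDCC will be unblinded after the Day 29 database lock".

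**The concern.** One endpoint carries the two-sided 0.05, and every later test in the Section 6.8 sequence depends on it. Two sections give it different timepoints and different data sources. One uses all daily scores up to a fixed day; the other uses the score from one visit, which may be made after that day. Section 3.3.2 itself warns that the two bases may disagree. The visit-based wording also recurs in the shell for the primary table, so it is not confined to one sentence.

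The cross-references lead a programmer to the wrong rule. Section 3.3.3 cites Section 3.3.4 for a dating rule that is not there, and Section 8.1.2.2 cites Section 3.3.4 for an endpoint defined in Section 3.3.5.

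The timing of the committee's Day 60 reviews is a separate and smaller matter. If the SAP does not say when those decisions become final, a reader cannot tell whether every primary classification was fixed before the sponsor and coordinating centre knew the treatment codes.

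**Working it through.** **1. Three subjects under each rule.**

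- *Subject A:* Category 7 on Day 10, alive and in Category 5 at the Day 29 visit. Section 3.3.3: event at 10 - 1 = 9 days. Section 3.3.4 read literally: the visit score is 5, so no event.
- *Subject B:* no Category 7 or 8 through Day 29, intubated on Day 30, Study Visit Day 29 made on Day 31 with Category 7 recorded. Sections 3.3.2 and 3.3.3: censored at Day 29 (28 days), no event. Section 3.3.4: event. Section 3.3.2 gives this kind of case as its own example of a mismatch.
- *Subject C:* dies on Day 20. Event under both rules.

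On the literal reading, groups A and B are classified differently. On the mildest reading, where Section 3.3.4 only moves the closing date to the visit, group A agrees and group B still differs.

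**2. Which rule the rest of the SAP supports.** Section 3.3.2 assigns time-to-event endpoints to actual days, and Section 3.3.3 defines the primary as time-to-event. Section 3.3.3 censors at Day 29 only if Category 7 never occurred, so subject A is an event there. Section 6.1 uses a time variable and a censoring variable. Section 8.1.1 needs event times up to t = 28, which a single visit score cannot supply. Section 3.3.4 stands alone apart from the table and section labels noted above.

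**3. The plan's own figure.** Inputs from Section 5: 0.85 versus 0.90, N = 1382, two-sided 5%. Equal arms of 691 are assumed, because the SAP does not state the allocation ratio.

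- Unpooled variance (Greenwood without censoring): SE = sqrt[(0.85 x 0.15 + 0.90 x 0.10)/691] = 0.0177; 0.05/0.0177 = 2.82; power = Phi(2.82 - 1.96) = 80.5%, as stated in Table 1.
- Pooled null variance: 80.3%, against the stated 80% for the exact test.

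The power calculation is sound and does not depend on the contradiction.

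**4. Illustration of the literal reading only.** Assume that a fraction f of events is of type A and is lost equally in both arms. Event rates become 0.15(1 - f) and 0.10(1 - f); power uses the pooled formula at 691 per arm.

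| f | Events, dexamethasone vs baricitinib | Difference (points) | Power |
|---|---|---|---|
| 0 | 104 vs 69 | 5.0 | 80.3% |
| 10% | 93 vs 62 | 4.5 | 75.5% |
| 20% | 83 vs 55 | 4.0 | 69.8% |
| 30% | 73 vs 48 | 3.5 | 63.4% |
| 40% | 62 vs 41 | 3.0 | 56.3% |

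Nothing in the SAP fixes f. The table shows how sensitive the analysis would be under that reading; it does not estimate what will happen. Group B cannot be sized at all from the document.

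**5. Day 60 data.** Under Section 3.3.3, a subject discharged to hospice before Day 29 with unknown death date is an event at discharge if Day 60 data are unavailable. If Day 60 was completed, the committee decides. Day 60 data can therefore affect primary status. Section 4.2.6 puts the Day 29 lock and the unblinding of DMID and the SDCC ahead of the Day 60 lock. No section dates the committee's decisions relative to that unblinding.

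**The case against.** The strongest reply is that the SAP already resolves the conflict. Section 3.3.2 works as a sorting rule, Section 3.3.3 gives detailed event and censoring rules, and the Section 8.1.1 statistic cannot be computed from one visit score. A careful programmer would follow Section 3.3.3. This stands, and it rules out a stronger reading that someone might infer: that the primary event set is open and turns simply on which section is programmed. It does not make Section 3.3.4 correct. That section names the primary endpoint twice and excludes the actual day, so it cannot be reconciled as written.

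A reader might also compare an assumed share of reclassified subjects with the planned 5-point difference and conclude that the effect could disappear. That comparison fails. The first is a share of all subjects and the second a contrast between arms. Equal proportional loss shrinks the contrast but does not remove it.

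Finally, a reader might infer that the event set is not frozen at unblinding. The documents do not say so. The committee is described as blinded, Section 4.2.6 does not list it among those unblinded, and Section 6.2.2 runs the final analyses on the database locked through Day 29. The Day 60 provision also covers a limited group of subjects. What remains is that the timing is unstated.

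**Conclusion.** The contradiction is real and sits in current text. Section 3.3.4 misstates the timepoint and data source of the primary endpoint, and the labels in Table 15, Table 23 and Section 8.1.2.2 carry the same visit-based wording. The intended definition is clear from the rest of the SAP: any Category 7 or 8 on or before actual Day 29. The practical risk is misclassification if Section 3.3.4 is followed: types A and B on the literal reading, type B alone on the mildest. Its size is unknown because the SAP gives no counts; the power table rests on an assumed f, equal loss in both arms and equal allocation. Sample size, alpha and test statistic are unaffected.

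The committee point is a lesser gap in stated timing. It is not evidence that adjudication takes place after unblinding.

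**What to change.** 1. In Section 3.3.4, remove the primary endpoint from the opening sentence and from the sentence assigning it to Study Visit Day 29. State that it follows Section 3.3.3, using the first date of Category 7 or 8 on or before actual Day 29 (t = 28).
2. In the Table 15 and Table 23 footnotes and in Section 8.1.2.2, replace the reference to the Day 29 study visit with Day 29. Correct the references to Section 3.3.4 in Sections 3.3.3 and 8.1.2.2 at the same time.
3. State that all Endpoint Review Committee decisions affecting Day 29 status, including those using Day 60 data then available, are final before DMID and the SDCC are unblinded. Use later Day 60 information only in a labelled sensitivity analysis.

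Items 1 and 2 cost only wording; N = 1382 and about 80% power stand. Item 3 needs the committee's last relevant meeting scheduled before the unblinding. Its small downside is that Day 60 information arriving later cannot inform the primary analysis.

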3.3.6. Time to Death

For analysis of time to death, the time to death will be defined as the elapsed time (in days) from randomization to death. For the safety analysis, this will be elapsed time (in days) from the first dose of study treatment (baricitinib, dexamethasone, remdesivir, or placebo).

Any subjects that are lost to follow-up or terminated early prior to death will be censored at the day of their last observed assessment or last captured event (e.g. the end date of an adverse event). Subjects who complete follow-up will be censored at the earliest of their Study Visit Day 29 and (actual) Day 29. Deaths that occur after Day 29 will be censored at Day 29.

Similar censoring methods will be used for the 14-day mortality analyses in that deaths that occur after Day 15 will be censored at Day 15 and subjects who are confirmed alive through Day 15 will be censored at Day 15. Subjects whose last observed assessment or last capture event (e.g., the end date of an adverse event) is prior to Day 15 will be censored at that last observed assessment/event.

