3.3.8. Time to Clinical Status Improvement

Several Secondary Endpoints involve evaluation of the time to improvement of at least one or two points on the clinical status 8-point ordinal scale. The time to improvement will be defined as the elapsed time (in days)

from randomization to the earliest day of observed improvement. Note that since clinical status assessments are recorded as defined in Section 4.3, the day that is being assessed (not necessarily the day the response is collected) will be used to determine the timing of events.

For analyses of this endpoint, imputation of the clinical score may be performed following the rules described in Section 6.5.

Any subjects that are lost to follow-up or terminated early prior to an observed improvement will be censored at the day of their last observed Clinical Status score. Subjects who complete follow-up but do not experience improvement will be censored at the day of their Study Visit Day 29. All deaths that occur on or before Study Visit Day 29 (and prior to any observed improvement) will be considered censored at Day 29.

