6.5. Missing Data

All attempts will be made to collect all data per protocol. Any data point that appears to be erroneous or inexplicable based on clinical judgment will be investigated as a possible outlier. If data points are identified as outliers, sensitivity analyses may be performed to examine the impact of including or excluding the outliers. Any substantive differences in these analyses will be reported.

For time to event outcomes, subjects who are lost to follow-up or terminate the study prior to Day 29 and prior to observing/experiencing the event will be censored at the time of their last observed assessment. Other rules for censoring are listed for the specific endpoint in Section 3.3.

For the analysis of the key secondary outcome, subjects who are discharged but are subsequently re-admitted prior to Day 15 without a reported clinical ordinal score, their clinical ordinal score will be imputed at 7, which is the highest value for a hospitalized subject.

For the analyses of the secondary outcomes that involve clinical score (i.e. the key secondary outcome and time to improvement), if a subject is discharged from the hospital (but not to hospice or other end-of-life care) without a previously or concurrently reported clinical score of 1 or 2, then their clinical score at the time of discharge will be imputed as 2, which is the highest value for a non-hospitalized subject. If a subject terminates early from the study while they are hospitalized or completes the study while still hospitalized, the last observed clinical score assessment will be used as their final assessment.

For the modified version of the ordinal score described in Section 4.3, if a subject is discharged from the hospital without a previously or concurrently reported clinical score of 2 or 3, then their clinical score at the time of discharge will be imputed as 3, which is the highest value for a non-hospitalized subject.

For the analyses of the secondary outcomes described in Section 3.3, the following imputation rules will be used for subjects who are lost to follow-up, terminate early from the study, or do not have further outcome data available after discharge for any reason:

- Days of Non-Invasive Ventilation/High-Flow Oxygen:

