8.1.2. Hierarchical Sequence of Secondary Endpoints Analyses

Analyses described in this section will be subject to the fixed-sequence hierarchical testing procedure described in Section 6.8. Any reference to p-values in this section is conditional on preceding hypothesis tests in the hierarchy.

If a superior test fails to reject the null hypothesis, the analyses will still be performed to provide estimated effects with confidence intervals for relevant statistics and associated confidence-interval by-arm, but p-values will not be generated. Confidence intervals for all analyses of secondary endpoints, will be 95% confidence intervals.

8.1.2.1. Clinical Status Ordinal Scale at Day 15

In the mITT population, the distribution of the 8-point Clinical Status ordinal score at Study Visit Day 15 (not necessarily actual study day 15), will be analyzed using a proportional odds model with treatment arm and actual baseline ordinal score (baseline ordinal score 5 or baseline ordinal score 6) as covariates. The treatment odds ratio estimated from the model will be presented along with the p-value, (Table 21). This analysis will be repeated for the As Treated population (Table 22). The Study Visit Day 15 clinical status score will be depicted graphically using shifted bar plots; the outcomes will be presented by actual baseline ordinal score and treatment group (Figure 13).

8.1.2.2. Proportion of Subjects Not Progressing to Clinical Status 6, 7, or 8 by Day 29

In the mITT population and among only those with an actual baseline ordinal score of 5, the proportion of subjects not progressing to ordinal score 6, 7, or 8 by Day 29 (see Section 3.3.4) will be analyzed using the same modeling approach as the primary outcome and described in Section 8.1.1. Kaplan-Meier curves (Figure 31) and p-values with estimates of proportions at the Day 29 study visit will be calculated and accompanied by confidence intervals (Table 23).

8.1.2.3. Mortality by Day 29

Mortality through Day 29 will be analyzed as a time to event endpoint (see Section 3.3.5). A table will present median time to event along with 95% confidence intervals overall for each treatment arm along with the hazard ratio estimate and log rank p-values. Differences in time-to-event endpoints by treatment will be summarized with Kaplan-Meier curves (Figure 27).

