Table 39: Clinical Status Scores by Treatment Group and Study Visit, Imputed – mITT Population, Actual Baseline Ordinal Score 5 or 6

Study Visit	Ordinal Scale Measure	Baricitinib + PBO + RDV (N=X)			PBO + Dexamethasone + RDV (N=X)			Risk Difference	
		n	%	95% CI	n	%	95% CI	%	95% CI
Day 1	Death at or before Study Visit (8)	x	x	x.x, x.x	x	x	x.x, x.x	x.x	x.x, x.x
	Hospitalized, on invasive mechanical ventilation or ECMO (7)	x	x	x.x, x.x	x	x	x.x, x.x	x.x	x.x, x.x
	Hospitalized, on non-invasive ventilation or high flow oxygen devices (6)	x	x	x.x, x.x	x	x	x.x, x.x	x.x	x.x, x.x
	Hospitalized, requiring supplemental oxygen (5)	x	x	x.x, x.x	x	x	x.x, x.x	x.x	x.x, x.x
	Hospitalized, not requiring supplemental oxygen - requiring ongoing medical care (COVID-19 related or otherwise) (4)	x	x	x.x, x.x	x	x	x.x, x.x	x.x	x.x, x.x
	Hospitalized, not requiring supplemental oxygen - no longer requires ongoing medical care (3)	x	x	x.x, x.x	x	x	x.x, x.x	x.x	x.x, x.x
	Not hospitalized, but new or increased limitation on activities and/or requiring new or increased home oxygen (2)	x	x	x.x, x.x	x	x	x.x, x.x	x.x	x.x, x.x
	Not hospitalized, no limitations on activities (1)	x	x	x.x, x.x	x	x	x.x, x.x	x.x	x.x, x.x
[Repeat for Study Visit Days 3, 5, 8, 11, 15, 22, and 29]									

N = Number of Subject in the mITT Population.

n = Number of subjects who reported the respective score

95% CI calculated using Wilson CIs

Programming Note: If necessary, a row for “No clinical status score reported – Completed study without reporting score” will be added as the last row for each day.

Table 40: Summary of Clinical Status Score by Treatment Group and Study Visit – mITT Population, Actual Baseline Ordinal Score 5 or 6

Study Visit	Statistic	Baricitinib + PBO + RDV (N=X)	PBO + Dexamethasone + RDV (N=X)	Difference
Baseline	Number of reported clinical scores	x	x	--
	Mean (95% CI)	x.x (x.x, x.x)	x.x (x.x, x.x)	x.x (x.x, x.x)
	Median	x.x	x.x	x.x (x.x, x.x)
	Range (Min, Max)	x, x	x, x	--
Day 3	Number of reported clinical scores	x	x	--
	Mean (95% CI)	x.x (x.x, x.x)	x.x (x.x, x.x)	x.x (x.x, x.x)
	Median	x.x	x.x	x.x (x.x, x.x)
	Range (Min, Max)	x, x	x, x	--
	Change from Baseline Mean (95% CI)	x.x (x.x, x.x)	x.x (x.x, x.x)	--
Continue for Days 5, 8, 11, 15, 22, 29				
N = Number of subjects in the mITT Population.				
Missing values were imputed using Last Observation Carried Forward. Clinical scores of 8 were carried forward from the date of death for subjects who died.				

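### Hospice discharges are handled inconsistently: scored as improved on the modified scale, and censored for Day 29 mortality where the primary analysis counts an event

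*SAP*

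**What the plan says.** Primary endpoint (SAP 3.3.3). When a patient goes to hospice or similar care before Day 29 and the date of death is not known, the event time, "with Day 60 data unavailable, will be the number of days from randomization to discharge". Both conditions must hold: no death date and no Day 60 data. Where Day 60 was completed, a different route applies and the blinded Endpoint Review Committee decides: patients "discharged to hospice or other end-of-life care prior to Day 29 with a death date unknown but completing Day 60 will be reviewed".

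Mortality (SAP 3.3.6 and 8.1.2.3). "Mortality through Day 29 will be analyzed as a time to event endpoint", and it is the fourth test in the fixed sequence of 6.8. The censoring rule is general: "Any subjects that are lost to follow-up or terminated early prior to death will be censored at the day of their last observed assessment" or, alternatively, at the last captured event. Section 3.3.6 mentions neither hospice nor committee review.

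Imputation at discharge (SAP 6.5). On the main 8-point scale, a discharged patient with no reported score of 1 or 2 is given a 2, and discharges to hospice or other end-of-life care are expressly left out. The parallel sentence for the modified scale applies "if a subject is discharged from the hospital without a previously or concurrently reported clinical score of 2 or 3" and gives a score of 3. It contains no hospice exclusion.

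Time to recovery (SAP 3.3.7) refers hospice discharges to the Endpoint Review Committee.

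**The concern.** The SAP recognises in 3.3.3, in 3.3.7 and in the main-scale rule of 6.5 that a discharge to end-of-life care is not an ordinary discharge. That recognition is missing in two places.

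On the modified scale, a patient sent to hospice is credited with a clear improvement on the day of discharge. This is the reverse of what the discharge means.

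In the mortality analysis, a patient with no further data leaves the risk set at the last contact. Kaplan-Meier and log-rank methods then assume that this patient's later risk of death equals that of the patients still under observation. For someone discharged to end-of-life care that assumption is not credible, so the estimated mortality is too low if such patients die by Day 29. If they are spread unevenly over the arms, the treatment comparison could move as well.

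**Working it through.** **1. One patient through the rules.** Take baseline score 5 or 6, discharged to hospice before Day 29, no death date, no Day 60 data, no earlier improvement recorded.

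- Primary analysis (3.3.3): event, timed at discharge.
- Day 29 mortality (3.3.6): censored at the last assessment or captured event.
- Time to improvement, main scale (6.5, 3.3.8): no score of 2 is imputed. A patient who has "terminated early prior to an observed improvement will be censored at the day of their last observed Clinical Status score" gains no credit for improvement.
- Time to improvement, modified scale (6.5, 8.2.6, Table 37): scored 3 at discharge. From 5 this is 5 − 3 = 2 categories better; from 6 it is 6 − 3 = 3. The patient is an event in both the one-category and the two-category analysis.

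The last two lines differ only because the hospice exclusion appears in one sentence of 6.5 and not in its counterpart.

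**2. Size of the mortality effect (illustration).** The SAP states no hospice rate and no expected mortality, so there is no figure of its own to reproduce on this point. The only SAP figure used is the total of 1382 in section 5, to set the arm size. It can be checked with n per arm = [1.96·√(2·0.875·0.125) + 0.842·√(0.85·0.15 + 0.90·0.10)]² / 0.05² = 686, or 1372 in total. That agrees with the 1382 the SAP obtained from an exact test.

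Assumptions: 1:1 allocation, so 1382/2 = 691 per arm; documented deaths of 3%, 5% or 10% spread evenly over days 3 to 27; H hospice discharges on day 10; no other censoring; every hospice patient dies by Day 29.

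Formula: mortality = 1 − Π(1 − d_t/n_t). In the censored version the H patients leave n_t after day 10. In the counted version they enter d_t on day 10, and the estimate reduces to (D + H)/691.

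| Documented deaths D | H | Censored | Counted as deaths | Difference (points) |
|---|---|---|---|---|
| 35 (5%) | 0 | 5.07% | 35/691 = 5.07% | 0.00 |
| 35 | 3 | 5.08% | 38/691 = 5.50% | 0.42 |
| 35 | 7 (about 1%) | 5.10% | 42/691 = 6.08% | 0.98 |
| 35 | 14 (about 2%) | 5.14% | 49/691 = 7.09% | 1.95 |
| 21 (3%) | 7 | 3.06% | 28/691 = 4.05% | 0.99 |
| 69 (10%) | 7 | 10.06% | 76/691 = 11.00% | 0.94 |

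Moving the discharge to day 5 or day 20 keeps the difference for H = 7 between 0.92 and 1.00 points. A hand check bounds it: with D = 35 the censored estimate must lie between 35/691 = 5.07% and 35/684 = 5.12%, so the gap to 6.08% is about 1 point.

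**3. Treatment comparison.** With 35 documented deaths in each arm, the crude ratio of deaths (baricitinib to dexamethasone) is 35/35 = 1.00 under censoring. Counting hospice patients as deaths gives 42/42 = 1.00 if they split 7 and 7, 35/42 = 0.83 if 0 and 7, and 42/35 = 1.20 if 7 and 0. The SAP contains nothing from which to choose among these.

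**The case against.** The strongest reply is that the two endpoints may properly differ. The primary is a composite of ventilation or death, where an unknown outcome after hospice discharge can reasonably count as failure; a mortality analysis may reasonably count only documented deaths. This stands. A reader might infer that the testing hierarchy contradicts itself, but the documents do not support that. Each test has its own defined endpoint, and the fixed sequence in 6.8 controls type I error whatever censoring rule is used. The modified scale and time to improvement lie outside that sequence.

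The second reply is that few patients can be affected, and this also stands. Section 4.1 provides contacts at Days 15, 22 and 29, by phone if necessary, and at Day 60, with chart review allowed when the Day 60 call fails. A patient must be missed by all of these.

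Three further readings are tempting but not supported:

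- That the patient is carried as alive to Day 29. Section 3.3.6 removes the patient at the last contact; the fault is informative censoring.
- That expected deaths become recoveries on the modified scale. Section 3.3.7 sends hospice discharges to the committee, and 8.2.5 repeats the recovery analysis without withdrawing that review. The flaw is shown for time to improvement only.
- That the Day 15 score stays at 5 or 6 by carrying the last value forward. The carry-forward rule in 6.5 covers patients who terminate or complete while still hospitalised. The footnote "Missing values were imputed using Last Observation Carried Forward" belongs to Table 40, a descriptive summary, not to the proportional odds test.

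None of this explains why the exclusion is missing from the modified-scale sentence, or makes the mortality censoring non-informative.

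**Conclusion.** The point holds in two parts. The modified-scale rule in 6.5 wrongly credits hospice discharges with an improvement of at least two categories; this reaches only the sensitivity analysis in Table 37. In the fourth hierarchical test, 3.3.6 censors informatively a patient whom 3.3.3 counts as an event at discharge, so the mortality level is biased downward if such patients die by Day 29.

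The up-to-1-point effect per 1% of an arm rests wholly on the assumed death rates, hospice rates, discharge days and death of every such patient by Day 29. A reader might infer that the comparison between arms is biased in a known direction. It is not: the direction and size depend on an imbalance about which the SAP gives no information, and with balanced numbers in the illustration the ratio does not move.

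**What to change.** In 6.5, add to the modified-scale sentence the same exclusion of hospice and other end-of-life discharges that the main-scale sentence carries.

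Keep the 3.3.6 definition as the main mortality analysis. Beside it, pre-specify a sensitivity analysis in which a hospice or other end-of-life discharge before Day 29, with unknown death date and no Day 60 data, counts as a death on the day of discharge. Report the number of such patients by arm with both results.

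The cost is a phrase in 6.5, a sentence or two for mortality and one extra mortality run. The drawback is that a few deaths in that run are presumed rather than documented, which is why it should stand beside the main analysis and not replace it.
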